### **1.3. Risk/Benefit Assessment**

Lenabasum is an investigational product not currently approved outside of clinical trial use; therefore, individual subjects may or may not experience a benefit from lenabasum for the disease condition under study. Subjects who receive placebo are unlikely to receive any benefit from participation in the study other than a potential placebo benefit and an opportunity to participate in the open-label extension (OLE) study. Individual subjects should carefully consider the risks versus benefits from participation in this clinical trial before signing the informed consent (IC).

In multiple nonclinical studies, cells isolated from patients with inflammatory / fibrotic diseases, animal models of disease, and mechanism of action studies conducted in healthy volunteers, lenabasum has demonstrated the potential to resolve innate immune responses as well as fibrotic processes. Efficacy signals have been observed in Phase 2 studies in SSc (JBT101-SSc-001), CF (JBT101-CF-001) and DM (JBT101-DM-001). Evidence of on-target biologic effects of lenabasum has been shown in the skin in DM and SSc subjects and in sputum from CF subjects, supporting potential clinical benefit. Efficacy signals have also been observed in subjects with

refractory traumatic neuropathic pain (CPL7075/02/01/001/1). Anticipated AEs in clinical trials with lenabasum include those related to the subject population being studied, concomitant medications that subjects may be taking (e.g., immunosuppressive medications) and lenabasum.

To date, the majority of AEs related to lenabasum have been mild in severity; serious adverse events (SAE) considered related to lenabasum have primarily been infective pulmonary exacerbations in subjects with CF. The most frequent AEs thought to be causally related to lenabasum (within 1-60 mg dose range) by the investigators include dry mouth and dizziness. The most frequent AEs observed in study subjects who received lenabasum in the 1-60 mg dose range, independent of relatedness to lenabasum, included fatigue, upper respiratory tract infection, infective pulmonary exacerbation (in subjects with CF), dry mouth, dizziness, cough, hemoptysis (in subjects with CF), and headache. Other AEs listed as class effects of CB1/CB2 agonists (e.g., , feeling drunk or abnormal or jittery, hot or hot and cold or cold, hangover, feeling relaxed or feeling of movements slower than normal) have been reported in < 5% of lenabasum-treated subjects.

[figure not shown]
Lenabasum has shown to inhibit human ether a-go-go (hERG) current with an  $IC_{50}$  value of 7  $\mu\text{mol/L}$  (2800 ng/ml). This concentration is  $\geq 146\times$  higher than the maximum free therapeutic concentration of 20 mg lenabasum twice-daily (BID) in humans, indicating a low liability for causing torsade de pointes ([Redfern et al, 2003](#)). In initial safety and tolerability studies, prolongations of QTc were observed using single electrocardiogram (ECGs); however, no QTc exceeded 500 msec (maximum QTc observed was 487 msec) and all were considered not clinically significant. In the SSc (JBT101-SSc-001) and CF (JBT101-CF-001) studies, triplet standardized ECGs with QT/QTc interval measurements showed no prolongation of QTc intervals or other significant ECG findings compared with placebo. QT/QTc intervals will be measured in this study. Convulsions consistent with CB1 effect on the brain have been observed in some non-clinical studies; however, lenabasum did not lower seizure threshold in a study done in rats specifically to evaluate the effect of lenabasum on seizure potential. No convulsions/seizures have been observed in any clinical studies done to date. Ataxia was observed at high doses in rats and mice and at  $\geq 10 \text{ mg/kg/day}$  in dogs where plasma exposures were approximately  $7.6\times$  higher than the anticipated maximum area under the curve (AUC) exposure achieved with lenabasum 20 mg BID (40 mg total daily dose). Ataxia has not been observed in humans.

Lenabasum has been found to be well-tolerated in clinical studies conducted to date with only mild or moderate AEs related to lenabasum observed. Together, results from the preclinical safety, toxicology and pharmacokinetic (PK) studies, efficacy studies in animal models of disease, studies with human biomaterials, and safety and preliminary efficacy data in humans support a favorable benefit-risk profile of lenabasum. These results support further study of lenabasum as a treatment for rare and serious inflammatory and fibrotic diseases with significant unmet medical need.

Additional information about the known and expected benefits and risks and reasonably expected AEs of lenabasum may be found in the [Investigator's Brochure](#).

## 2. OBJECTIVES AND ENDPOINTS

Primary Objective	Primary Efficacy Endpoint
To evaluate the efficacy of lenabasum compared to placebo in subjects with dermatomyositis (DM)	
TIS by the 2016 American College of Rheumatology (ACR)/European League Against Rheumatism (EULAR) Myositis Response Criteria at Week 28
 
The TIS is comprised of 6 core set measures and absolute value and change from baseline in each core set measure will be presented to support the composite TIS:
 

1. Physician global activity (MDGA)

2. Patient global activity (PtGA)

3. Manual Muscle Testing (MMT)

4. Health Assessment Questionnaire (HAQ)

5. Muscle enzymes

6. Extramuscular global activity (EMGA)

 
A MMT that assesses strength in 8 muscle groups (MMT-8) will be used in this study.

Secondary Efficacy Endpoints	
	
The following endpoints will be compared in lenabasum 20 mg BID and to placebo cohorts and lenabasum 5 mg BID compared to placebo cohorts at Week 28, unless otherwise specified.
 
All outcomes involving continuous variables will be assessed as absolute values and, if relevant, change from Baseline. All categorical variables will be assessed as number and proportion of subjects in each category:
 

1. Subjects who achieve Definition of Improvement (DOI)

2. Subjects who improve by at least one category on the Investigator Global Assessment (IGA) scale of skin activity

3. Subjects who achieve TIS <math>\geq 40</math> (at least moderate improvement)

4. TIS in subjects receiving any immunosuppressant medication for <math>> 1</math> year at Baseline

5. TIS at Visit 10 (Week 52)

6. Cutaneous Dermatomyositis Disease Area and Severity Index (CDASI) activity score

7. TIS (lenabasum 5 mg compared to placebo cohorts only)

	
[REDACTED]
 
[REDACTED]
 
[REDACTED]
 
[REDACTED]
 
[REDACTED]
 
[REDACTED]
 
[REDACTED]

Secondary Objective	Safety Endpoints
To evaluate the safety and tolerability of lenabasum in subjects with DM	

1. Adverse events (AEs)

2. Changes in vital signs, physical examinations, blood and urine laboratory safety tests, and ECGs associated with lenabasum treatment

3. Number of subjects who permanently discontinue study product due to AEs probably- or definitely-related to treatment

Tertiary Objectives	Tertiary Endpoints and Evaluations
[REDACTED]	
[REDACTED]
 
[REDACTED]
 
[REDACTED]
 
[REDACTED]

[REDACTED]	
[REDACTED]
 
[REDACTED]

[REDACTED]	
[REDACTED]
 
[REDACTED]
 
[REDACTED]

[REDACTED]	
[REDACTED]

Additional Objectives	Additional Endpoints
To evaluate the long-term efficacy and safety of lenabasum in completed subjects who continue to receive treatment in an optional open-label extension (OLE)	In an open-label extension (OLE) phase (Part B): 

1. Evaluate long-term signals of efficacy

2. Evaluate long-term safety

[figure not shown]
Endpoints will be finalized in the statistical analysis plan (SAP) prior to unblinding.

### 3. STUDY DESIGN

#### 3.1. Overall Design

This is a Phase 3, multicenter, interventional, study designed to assess the efficacy and safety of lenabasum in subjects with DM. The study consists of two parts: Part A is a double-blind, placebo-controlled phase. Part B is an optional OLE phase with a single treatment arm. The overall design for this study is presented in Figure 1.

**Figure 1: Study Design for JBT101-DM-002**

Abbreviations: BID = twice daily, DB = double blind, OLE = open label extension, PC = placebo controlled

##### 3.1.1. Part A: Double-Blind, Placebo-Controlled Phase

The initial plan is for approximately 150 dosed subjects to receive at least 1 dose of study product. The final number of subjects to be dosed will be decided after a blinded interim analysis. The timing and methods for the interim analysis will be outlined in the SAP. It is expected that approximately 200 subjects will be screened to dose 150 subjects.

Subjects will be randomized to receive lenabasum 20 mg, lenabasum 5 mg, or placebo BID in a 2:1:2 ratio. It is hypothesized that subjects receiving lenabasum will experience greater improvement in the TIS score at Week 28 compared to subjects receiving placebo.

The total subject duration is approximately up to 60 weeks and includes the following: a screening visit (up to 4 weeks prior to Visit 1), up to a 52-week treatment period, and a Safety Follow-up Visit that will be conducted 4±1 weeks after the last visit. Subjects will be assessed for safety and efficacy parameters every 6 weeks except for Visit 2, which will occur 4 weeks after Visit 1, for a total of up to 10 treatment visits. Study personnel will contact subjects by telephone about halfway between Visit 9 and Visit 10 (Week 49 ± 1) to assess compliance, safety and overall status of DM, if applicable.

A subject's corticosteroid or other immunosuppressant treatments may be reduced if the investigator determines that clinical improvement in the subject's DM has occurred and a reduction is warranted. It is recommended that a reduction in corticosteroid or immunosuppressant treatment should not occur prior to Visit 4 or after Visit 8. A preferred schedule for reduction is provided in [Section 5.5.1](#) of the protocol.

### **3.1.2. Part B: Optional Open-label Extension**

Upon completing Part A (Visit 10), at the investigator's discretion, consenting subjects may directly rollover into the optional OLE Phase (Part B). All subjects in the OLE will receive lenabasum 20 mg BID (see [Table 4](#)).

Subjects will continue their standard of care treatment as in Part A. Subject's corticosteroid or other immunosuppressant treatments may be reduced during this study if the investigator determines that clinical improvement in the subject's dermatomyositis has occurred and a reduction is warranted. A preferred schedule for reduction of corticosteroid is provided in [Section 5.5.1](#).

The OLE may be extended beyond 1 year. Sites will be notified by an administrative memo as to any extension and will inform their EC/IRB. The design of an extended OLE will follow the same design and procedures as described in Table 4. At the investigator's discretion, consenting subjects will rollover at the conclusion of Visit B8. The extension visits will be captured in the electronic data capture (EDC) as C1-C8 respectively.

Subjects who discontinue the study at any stage and for any reason will be encouraged to complete the procedures described in the Early Termination (ET) Visit as well as complete the Safety Follow-up Visit  $4 \pm 1$  weeks later.

The same efficacy and safety parameters described as primary and secondary objective for Part A will be evaluated in Part B as described in the SAP.

The results of Part B are expected to be analyzed after Part A results have been completed and will be reported as either an addendum to the clinical study report (CSR) or as a separate CSR.

### **3.1.3. Study JBT101-LTS-001: 2-year Observational Safety Follow-up**

Subjects who participated in Part A but are ineligible for the OLE (e.g., completed Part A and declined participation in the OLE, or subjects who discontinued from Part A for whatever reason), will be offered the opportunity to participate in a separate 2-year non-interventional safety surveillance study (Study JBT101-LTS-001).

## **3.2. Scientific Rationale for Study Design**

### **3.2.1. Part A: Double-blind, Placebo-controlled Phase**

In Part A, a double-blind, randomized, placebo-controlled design will be used. Part A will include up to 52-weeks of treatment to facilitate an unbiased assessment of the efficacy, safety and tolerability of lenabasum in the treatment of DM (see [Table 3](#)). Twenty-eight weeks treatment is expected to be sufficient to demonstrate long-term safety and efficacy of lenabasum compared to placebo, to support long-term use of lenabasum and 52-weeks treatment and OLE are expected to provide further evidence of long-term-safety and efficacy.

Subjects will be allowed to continue their current treatment, which will reduce the risk of disease flare precipitated by discontinuation of medication to meet entry criteria.

The primary endpoint chosen for this study is the TIS ([Aggarwal et al., 2017](#)) at 28 weeks. Because of heterogeneity in the organ-involvement in DM, organ-specific efficacy outcome does not reflect the extent of disease in DM. The TIS score is based on 6 core measures: patient and

physician global activity on a 10-cm VAS, muscle strength measured by MMT, physical function measured by the HAQ, extramuscular global activity (EMGA) measured by the physician on a 10-cm VAS, and the most abnormal serum muscle enzyme. Absolute value and change from Baseline in each core set measure will be provided to support the TIS assessment. The patients with DM targeted for inclusion in this study are those who reflect the totality of DM manifestations, making TIS a reasonable primary endpoint. Definition of Improvement (DOI), Investigator Global Assessment (IGA) scale of skin activity, TIS  $\geq 40$  (at least moderate improvement), TIS in subjects receiving any immunosuppressant medication for  $> 1$  year, TIS at Week 52, and Cutaneous Dermatomyositis Disease Area and Severity Index (CDASI) activity score are selected as secondary efficacy outcomes that provide additional measures of improvement on various aspects of DM disease. Change in corticosteroid dose and other immunosuppressives will be captured as a tertiary efficacy outcome, because long term side effects from systemic corticosteroids and other immunosuppressant medications pose a major safety risk to patients.

### **3.2.2. Part B: Open-Label Extension**

In Part B, all subjects will receive open-label lenabasum 20 mg BID. Similar efficacy and safety assessments will be performed at regularly scheduled visits (see [Table 4](#)) based on the scientific rationale for Part A.

### **3.3. Justification of Dose**

[REDACTED]

[REDACTED]

[REDACTED]

[REDACTED]

[REDACTED]

[REDACTED]

## 4. STUDY POPULATION

### 4.1. Inclusion Criteria

Subjects must meet ALL of the following criteria to be eligible for the study:

1. Able to understand and voluntarily sign the informed consent
2. Male or female  $\geq 18$  years of age at the time of signing the informed consent
3. Fulfill one of the following criteria for DM:
  - a. Bohan and Peter's criteria for probable or definite DM ([Bohan and Peter, 1975a](#); [Bohan and Peter 1975b](#))
  - b. ACR/EULAR criteria ([Lundberg et al, 2017](#))
4. Subject has active DM as determined by the investigator
5. Disease activity/severity fulfils one of the following three criteria:
  - i. MDGA  $\geq 3$  cm (0-10 cm scale) and MMT-8 score  $\leq 142$  (out of 150 total possible)
  - ii. Sum of MDGA, PtGA and EMGA VAS scores is  $\geq 10$  cm (all scales individually on 0-10 cm scale)
  - iii. MDGA  $\geq 3$  cm and CDASI activity score of  $>14$
6. Stable doses of immunosuppressive medications for DM as defined by:
  - a. Unchanged dose of oral corticosteroids  $\leq 20$  mg per day prednisone or equivalent for  $\geq 4$  weeks before Visit 1
  - b. Unchanged dose of immunosuppressive medications other than oral corticosteroids for  $\geq 8$  weeks before Screening
7. Willing to not start or stop any immunosuppressive medications for DM from Screening through end of study, unless a change is part of the protocol or considered in the subject's best medical interest by the site investigator or another physician who has primary responsibility for treating the subject's DM.
8. Willing to not use any cannabinoids, including recreational marijuana, medical marijuana and other prescription cannabinoids from Screening through end of study.
9. Able to adhere to the study visit schedule and other protocol requirements and follow study restrictions.
10. Women of childbearing potential (WOCBP) must not be pregnant or breastfeeding and they or their male sexual partner must be using at least one acceptable method of contraception (see [Appendix 1](#)) for at least 4 weeks before Visit 1 and be willing to continue its use for at least 4 weeks after discontinuation of study product.
11. Male subjects must be willing to follow acceptable contraceptive requirements (see [Appendix 1](#)) and should not get anyone pregnant while they are taking the study product or within 4 weeks after taking the last dose of the study product, during which time period they or their female sexual partner must be willing to use at least one recommended method of contraception.

## 4.2. Exclusion Criteria

Subjects are excluded from the study if any of the following criteria apply:

1. Unstable DM or DM with end-stage organ involvement at Screening or Visit 1, including:
  - a. On an organ transplantation list or has received an organ transplant, except corneal transplant
  - b. Interstitial lung disease requiring constant oxygen therapy. This excludes oxygen used to aid sleep or exercise
  - c. Pulmonary hypertension requiring constant oxygen therapy. This excludes oxygen used to aid sleep or exercise
  - d. Subjects requiring supplemental tube feeding or parenteral nutrition
2. Certain medications at Visit 1, including:
  - a. Treatment with intravenous or intramuscular corticosteroids within 4 weeks before Visit 1 (Note: treatment with intra-articular corticosteroids within 4 weeks before Visit 1 is allowed)
  - b. Treatment with oral or intravenous antibiotics or antiviral treatments for new bacterial or viral infections within 4 weeks of Visit 1. This does not include prophylactic antibiotics or antiviral treatments
  - c. Any investigational agent within 30 days or 5 therapeutic half-lives of that agent whichever is longer, before Visit 1
3. Significant diseases or conditions other than DM that may influence response to the study product or safety, such as:
  - a. Acute or chronic hepatitis B or C infection (see [Section 8.2.6](#))
  - b. Human immunodeficiency virus infection (see Section 8.2.6)
  - c. History of active tuberculosis or positive tuberculosis test without a completed course of appropriate treatment. Having already completed at least 1 month of appropriate treatment is eligible.
  - d. Evidence of cancer (except for treated basal or squamous cell carcinoma of the skin or cervical carcinoma in situ) within 3 years of Visit 1
4. Any of the following values for laboratory tests at Screening:
  - a. A positive pregnancy test in women of child-bearing potential (WOCBP) - also at Visit 1
  - b. Hemoglobin < 9 g/dL in males and < 8 g/dL in females
  - c. Neutrophils <  $1.0 \times 10^9/L$
  - d. Platelets <  $75 \times 10^9/L$
  - e. Creatinine clearance < 50 mL/ min/1.73 m^2 on screening blood test, per the Modification of Diet in Renal Disease Study or in 24-hour urine creatine clearance measurement
5. Any known hypersensitivity to lenabasum or any of its excipients.

6. Any medical, psychiatric or substance abuse condition, concurrent medical therapies, or abnormal laboratory values that in the opinion of the site investigator may put the subject at greater safety risk, influence response to study product, or interfere with study assessments.
7. Subjects who have been accommodated in an institution as a result of official or judicial decision.

When there is doubt as to subject eligibility, the investigator or qualified designee should discuss a subject's eligibility with the Medical Monitor.

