### 10.1.7. Safety Oversight

#### 10.1.7.1. Medical Monitoring

Medical Monitors have the responsibility to review key parameters to ensure eligibility prior to randomization of each subject as well as evaluate information relevant to the product safety throughout the development and implementation of the protocol. This data and safety review facilitates early detection of safety signals and maximizes the chances for continued appropriateness of the research and protection of human subjects. This oversight includes providing applicable recommendations about subject safety. The medical monitors will provide recommendations about subject safety to the Chief Medical Officer of Corbus, who, as appropriate, will report concerns about subject safety to other Corbus management staff.

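### Exclusion 3c grants its 1-month treatment relief without saying which tuberculosis group it covers, so read literally it clears a subject still being treated for active tuberculosis

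*Protocol*

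**What the plan says.** Exclusion 3 in Protocol Section 4.2 opens with "Significant diseases or conditions other than DM that may influence response to the study product or safety, such as" and then lists examples. Item 3c is the TB item. Its first sentence is "History of active tuberculosis or positive tuberculosis test without a completed course of appropriate treatment". Its second sentence declares that at least 1 month of suitable treatment makes a subject eligible. Where the two sentences meet, the text runs "without a completed course of appropriate treatment. Having already completed at least 1 month of appropriate treatment is eligible". The second sentence does not name a TB group, and it does not say by when the month must be complete.

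Four other provisions could bear on the same subject:

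- Exclusion 2b bars "Treatment with oral or intravenous antibiotics or antiviral treatments for new bacterial or viral infections within 4 weeks of Visit 1", and then adds "This does not include prophylactic antibiotics or antiviral treatments".
- Exclusion 6 bars, among other things, medical conditions and concurrent therapies that "in the opinion of the site investigator may put the subject at greater safety risk".
- The closing paragraph of Section 4.2 begins "When there is doubt as to subject eligibility, the investigator or qualified designee should discuss" and sends such cases to the Medical Monitor.
- Section 10.1.7.1 has Medical Monitors "review key parameters to ensure eligibility prior to randomization of each subject".

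None of the four mentions TB.

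**The concern.** A safety exclusion should give the safe answer on its own words. Here the first sentence asks for a finished course, and the second accepts one month of treatment without limiting who may use it. A site that takes the second sentence at face value would clear a subject with partly treated active TB, and would have no obvious reason to think the case doubtful.

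The setting makes this worth correcting. Section 4.1 allows oral corticosteroids up to 20 mg per day of prednisone or equivalent. Section 5.5 allows other background immunosuppressants, including cyclophosphamide and monoclonal antibodies. Section 5.5.2 allows immunosuppression to be increased or newly started after Visit 1 if the dermatomyositis worsens.

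There is also a procedural cost if two people read 3c differently. If a dosed subject is later judged ineligible, Section 4.4 calls for dosing to be discontinued. Section 10.1.10 lists failure to meet eligibility criteria at randomization among the major protocol violations.

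**Working it through.** No arithmetic applies. The check applies 3c to one subject and then looks for text elsewhere that settles the answer.

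**Step 1: the subject.** Take a person with active TB who has completed 1 month of treatment and whose course is not finished. Assume that TB now under treatment counts as a history of active TB.

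**Step 2: first sentence of 3c.** The subject has a history of active TB and no completed course. The sentence excludes the subject.

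**Step 3: second sentence of 3c.** The subject has completed at least 1 month of treatment. The sentence says that this is eligible. It directly follows a sentence about both groups and has no limiting words, so read literally it lifts the exclusion from step 2. The subject passes 3c.

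**Step 4: effect on the first sentence.** If the relief serves both groups, the completed-course requirement binds only subjects with less than 1 month of treatment. The relief makes better sense if it is confined to a positive test without active disease, but that limit is not written.

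**Step 5: look for the limit elsewhere.** Items 3a and 3b (hepatitis and HIV) refer to Section 8.2.6 for the test procedure. Item 3c has no such reference, and Section 8.2.6 does not discuss TB. The screening list in Section 7.2.1.1 and Table 3 names HIV, HBV and HCV testing, and nothing there explains 3c. No other place in the protocol text shown states a TB rule.

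**Step 6: set the other provisions beside the case.**

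| Provision | Could it stop this subject? | Does it settle 3c? |
|---|---|---|
| Stem of exclusion 3 | Yes, since its list is only of examples | No. It is general, while 3c speaks to TB directly |
| Exclusion 2b | Possibly | No. It reaches only new infections, and does not say whether TB treated for a month is still new |
| Exclusion 6 | Yes, if the investigator so judges | No. It rests on opinion |
| Medical Monitor, Section 4.2 | Yes, if someone sees a doubt | No. No TB rule is given to apply |
| Medical Monitor, Section 10.1.7.1 | Yes, if TB is among the parameters reviewed | No. The parameters are not listed |

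Each provision can stop the subject only by judgement or by an uncertain reading. None supplies the missing limit.

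**The case against.** The strongest reply is that passing 3c does not make anyone eligible. Section 4.2 excludes a subject if any one criterion applies, so the second sentence of 3c can lift 3c and nothing else. Partly treated active TB in a patient on immunosuppressants is a clear candidate for exclusion 6, and Medical Monitors look at every subject before randomization. This stands. A reader might infer from 3c that the protocol admits subjects with active TB to the trial. The documents do not support that. They show only that the one criterion written for TB lets such a subject through.

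A second reply concerns grammar. In the first sentence, the words about an unfinished course may attach only to the positive test. Any history of active TB would then exclude, treated or not, and the relief would naturally belong to the positive test. This reading is available, so the literal reading cannot be presented as the only one. It adds to the ambiguity rather than removing it. It also means that a rewrite expressly admitting completed active TB could loosen the criterion by accident.

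A third reply is that no document says 1 month is too short for active TB. That is so. The point rests on the protocol's own first sentence, which asks for a completed course and is then undone by the second.

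**Conclusion.** The concern holds as a drafting fault in a safety criterion. Taken literally, 3c passes a subject with active TB after 1 month of an unfinished course, and no other text in the protocol states a TB rule that corrects this.

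Severity is low. Few subjects can be affected, the documents give no count or risk figure, and discretionary provisions would probably stop many of those subjects. There is no effect on the endpoint, power or type I error. A reader might also infer a TB hazard specific to lenabasum. The protocol states none, and the argument does not need one.

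The conclusion rests on two assumptions: that TB now under treatment falls under a history of active TB, and that the sponsor did not intend to clear partly treated active disease. The second is likely, but only the sponsor can confirm it.

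**What to change.** Leave the first sentence of 3c unchanged. Replace the second with: *A subject with a positive tuberculosis test and no history of active tuberculosis who has completed at least 1 month of appropriate treatment before Visit 1 is eligible.*

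This removes the relief from active TB under either grammatical reading of the first sentence, keeps it for the positive-test group, and fixes when the month must be complete. Exclusion 2b needs no change, because it already exempts prophylactic treatment.

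Separately, the sponsor should confirm whether active TB with a completed course is meant to be eligible, and reword the first sentence only if the answer calls for it.

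The cost is one sentence in an amendment, with no new test or procedure. The downside is that a rare subject still being treated for active TB becomes ineligible.
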